5.4 Emergency Envelope/Emergency Unblinding Card

Emergency envelope is prepared for SAE happening, one opens the envelope to rescue in time, and avoid overall un-blinding. "A randomized, double-blind clinical study of Istaroxime", and the randomization number are printed on the envelopes. The emergency envelope draft is as follow:

Double-	blind clinical study emergency	
Un-blinding record Drug Randomization No.: Study project: A randomized, double-blind clinical study of Istaroxime		
_	Therapeutics Company Limited	
	esponsible Sites: XX	
The subject of the	nis Randomization No. is randomly divided into:	
	Test group: Istaroxime 0.5 mcg/kg	
	Test group: Istaroxime 1.0 mcg/kg	
	Control group: Placebo	
Reason for emergency unblinding:		
Study center:		
Signature of investigator: Date:		
Signature of principal investigator: Date: Note: the case should withdraw from the study after emergency un-blinding		

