5.2 Drug Blind Code

The computer generated randomization list stratified by centre and atrial fibrillation (Yes/No) will be prepared via a computerised method. Starting from the lowest number provided, in each center and and atrial fibrillation, at Day 1, patients will be sequentially assigned to the next randomization number, following the order in which they present themselves for the study. The investigator will keep the code break envelopes in a locked, secure storage facility.

A code break envelope can only be opened in an emergency situation (mainly SUSAR occurrence) where the investigator considers it essential to know which treatment the subject was taking. If possible, it is recommended that the investigator contacts the Sponsor before opening an envelope. The monitor shall be promptly notified when a treatment code envelope is opened. The investigator shall provide a certified explanation of why the treatment code was opened in the Case Report Form for the subject or directly on the opened treatment code envelope.

IMPORTANT: The randomization codes will only be disclosed to the laboratory in charge of the bioanalytical assay (plasma and urine PK assessment) of istaroxime and its metabolites, in order to prevent analyses of samples from patients who have received placebo. This laboratory will re-code identifiers of patients, allowing only to differentiate but not to identify the patients, in order to maintain blinding integrity for the other assessments of the study, until database lock. PK results will be maintained separate from the electronic CRF data until database lock at study completion.

Emergency Un-blinding: 1) Un-blinding condition: any emergencies of unknown origin that occur to the subject during the trial, should find out the medication type, or the subject asks to quit and wants to know the medication type; 2) Un-blinding register: the principle investigator opens and reads the emergency letter of corresponding number, recording the reading date and reason in detail, and signs his/her name; 3) Un-blinding disposal: once the emergency letter is **Protocol N°: CVT-CV-002**

read, the corresponding case is regarded as drop-out.

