IMPORTANT: An emergency code break by the Investigator may be authorized only in case of an unexpected serious adverse event (SUSAR), suspected to be related to an investigational product and requiring, according to the Investigator, the knowledge of the study treatment administered. In such a case, the following information must be documented in the e-CRF: reason for code break, date, name, qualification, patient initials and birth date (as recorded in the e-CRF) and electronic signature of the person who requested the code break. At completion of the study, all emergency code breaks tracked by the e-CRF will be checked for verification of the blinding integrity.

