6.2 Safety Endpoints

The following safety endpoints will be assessed during treatment and the post-treatment/follow-up periods:

- Incidence of adverse events;
- Change in vital signs (including body temperature and dyspnoea);
- Change in 12-lead ECG parameters;
- Incidence of clinically or hemodynamically significant episodes of supraventricular or ventricular arrhythmias detected by continuous ECG dynamic monitoring;
- Change in laboratory parameters (hematology, blood chemistry and urinalysis);
- Change in renal function;
- Change in cTnT;
- Incidence of cTnT elevation relative (>50% or >20% relative increase over the cTnT levels at baseline, for patients with cTnT basal levels at baseline < or ≥ of the 99% URL (upper reference levels, as defined for the Roche hs test in patients with normal renal function, eGFR ≥ 85 ml/min); in patients with eGFR below this value, the renal function variations must be considered in evaluating the significance of the cTnT changes);

• Mortality at Day 30.

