10. REPORTING OF ADVERSE EVENTS

10.1 Definition of Adverse Event (AE)

Adverse event (AE) is an adverse medical event that occurs following informed consent signature, the event is not necessarily related to the treatment. Therefore, adverse events may be any discomfort and unconscious signs (such as abnormal laboratory examination results), symptoms or illnesses.

- Any adverse event, whether serious or not, whether related to the treatment or not, should be recorded on the CRF.
- Investigator should follow up the patients that dropped out because of any adverse event until recovery, and record the date of AE occurring and recovering.
- If during adverse event follow-up, the adverse event progresses to an "SAE", or if a subject experiences a new SAE whose relationship to the study drug(s) cannot be ruled out, the investigator must immediately report the information to the sponsor.

Protocol N°: CVT-CV-002

Even if the subject does not return to normal or to his or her previous state, the follow-up can be considered finished when the following procedures have been taken:

- The investigator judges that the follow-up of the subject concerned is no longer necessary based on the progress made during the follow-up,
- The reason for such a judgment is entered as a comment on the case report form for the follow-up.

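### Declaring a code-broken patient a drop-out who leaves the study takes that patient out of scheduled data collection depending on outcome, and no visible text secures the later endpoints

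*Protocol*

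**What the plan says.** Two places fix the patient's status after an emergency code break. Protocol 5.2 says that once the letter is read "the corresponding case is regarded as drop-out". The card in Protocol 5.4, which the investigator signs, says "the case should withdraw from the study after emergency un-blinding". The card refers to the study, not only to study drug.

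The stated reasons for opening an envelope differ:

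- Protocol 5.4 describes the purpose in these words: "Emergency envelope is prepared for SAE happening, one opens the envelope to rescue in time".
- One paragraph of Protocol 5.2 says a code break "may be authorized only in case of an unexpected serious adverse event (SUSAR") and adds that the event must be suspected to be related to the product.
- Another paragraph of Protocol 5.2 is wider. It admits any emergency of unknown origin, and also the case where "the subject asks to quit and wants to know the medication type".

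On follow-up, Protocol 10.1 says "Investigator should follow up the patients that dropped out because of any adverse event until recovery". Protocol 9 monitors adverse events to 30 days after treatment end. Protocol 7 places a general duty on the investigator to try to ascertain outcomes between Day 5 and Day 30. None of the three mentions unblinded patients. The safety endpoints in Protocol 6.2 include "Mortality at Day 30".

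**The concern.** The code is broken mainly because something serious has happened, often something suspected to be a drug reaction. A rule that ends participation at that point removes patients from the schedule for a reason tied to outcome. If such reactions are more frequent on istaroxime, the removal will differ between arms. The endpoints exposed are the 24-hour E/Ea (primary), cTnT to 72 hours, worsening heart failure during the stay, cardiovascular readmission or emergency visit by Day 30, and Day-30 mortality.

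The SAP does not compensate. SAP 7.1 keeps missing values in the denominator of percentages, so an unrecorded death or readmission lowers the reported percentage. SAP 6.3 sets length of stay to 4 days when the days after Day 4 are missing, which can shorten the recorded stay of a patient who had a serious event. SAP 7.1 does not impute echocardiographic data, so a patient without a 24-hour echo is not in the primary ANOVA. The rule also reaches the data behind the escalation decision: Protocol 16.3 has the DSMB review cTnT elevation after Cohort I, and samples scheduled after a code break may not exist.

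**Working it through.** The plan gives no figure to reproduce: no expected number of code breaks and no formal sample-size calculation. The check is a comparison of texts, followed by simple proportions on assumed counts.

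**Step 1. What is kept for a code-broken patient?**

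| Data | Text that might keep it | Secured after withdrawal? |
|---|---|---|
| Course of the triggering event | Protocol 10.1, until recovery or until the investigator closes follow-up | Largely yes, including a death before recovery |
| Other adverse events to Day 30 | Protocol 9, item 1 | Not stated once the patient has left the study |
| 24-hour E/Ea | None | No |
| cTnT to 72 hours | None | No |
| Day-30 readmission and vital status | Protocol 7, general effort in Days 5 to 30 | Not secured; withdrawn patients are not mentioned |

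Section 10.5 (reporting of SAEs) was not available to check.

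**Step 2. Inputs.** Each cohort has 40 patients on istaroxime and 20 on placebo (Protocol 3). SAP 7.4 and 7.7.2 pool placebo across cohorts for all but the echocardiographic endpoints, giving 20 + 20 = 40. The number of code-broken patients with unknown Day-30 status, k, is assumed to lie between 1 and 4 per group of 40.

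**Step 3. Bound on Day-30 mortality.** With d known deaths among n patients, the lowest possible proportion is d/n and the highest is (d + k)/n. The width is k/n.

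- n = 40 (an istaroxime arm, or pooled placebo): 1/40 = 2.5 points, 2/40 = 5 points, 4/40 = 10 points.
- At the Cohort I interim, where cTnT elevation is reviewed with 20 on placebo, each placebo patient of unknown status is 1/20 = 5 points and each istaroxime patient 1/40 = 2.5 points.

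**Step 4. Direction under the SAP's denominator rule.** If m of the true deaths are not recorded and the patients stay in the denominator, the reported proportion falls by m/n. As an illustration with assumed counts, take 4 deaths among 40 (4/40 = 10.0%) with 2 unrecorded. The table shows 2/40 = 5.0%. Taking those two patients out of the denominator gives 2/38 = 5.3%, so the shortfall comes from the missing outcomes far more than from the denominator rule.

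No bias is calculated for E/Ea, because nothing in the documents indicates how 24-hour values in code-broken patients would differ from the rest.

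**The case against.** The strongest reply is that the loss is narrower than the two sentences suggest, and much of that reply stands.

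- A reader might infer that outcomes are lost for all patients with serious events. The documents do not support this. Only patients whose code is actually broken are affected, and the restrictive paragraph of Protocol 5.2 would make them few. Under the wider paragraph, some would be patients who were leaving anyway.
- A reader might infer that every later outcome disappears. That is also too strong. A death from the unresolved triggering event should be captured under Protocol 10.1. Protocol 10.2 makes hospitalisation a serious event, so some readmissions could surface as adverse-event data.
- A reader might count every placebo patient as 5 points throughout. That holds only at the Cohort I interim; the final mortality, readmission and cTnT summaries pool placebo to about 40.
- A reader might infer that the DSMB loses the evidence on these patients. The triggering event and the cTnT samples taken before the break remain, and the board reviews unblinded. Only later samples are at risk.
- A code break is not an exclusion from the ITT or safety set (SAP 5.1 and 5.3), SAP 7.1 shows a category for missing data, and mortality, readmission and worsening heart failure are summarised descriptively only.

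What the reply does not do is point to visible text that keeps the 24-hour echo, the remaining cTnT samples or Day-30 status for a withdrawn patient. The general effort in Protocol 7 is not specific to such patients, and a signed card telling the site to withdraw the patient gives it a reason to stop. A missing-data category shows the gap but does not recover the outcome.

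**Conclusion.** The point holds for patients whose code is broken. Protocol 5.2 and 5.4 end their participation, the main triggers are serious and often suspected drug-related events, and the provisions that soften the loss do not secure the primary endpoint, the cTnT series or Day-30 status.

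The size rests on an assumed 1 to 4 code-broken patients of unknown status per group of 40, which widens the Day-30 mortality bound by 2.5 to 10 points. At the interim, each placebo patient is 5 points. The real number could be zero, in which case nothing is lost.

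The change should be made because it is cheap and the loss, if it occurs, is selective and falls on safety outcomes. Confidence about what is not kept is moderate, since Section 10.5 could contain a follow-up duty. Such a duty would still have to be squared with the two explicit instructions.

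**What to change.** In Protocol 5.2 and on the card in 5.4, replace the drop-out and withdrawal sentences with one rule on data collection. After an emergency code break the patient remains in the study for all scheduled assessments and the Day-30 outcome unless consent is withdrawn, is analysed in the ITT and safety sets under their existing definitions, and is flagged as unblinded in the data.

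Two related matters are for the sponsor to settle separately:

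- The paragraphs of Protocol 5.2 conflict on when a code may be broken and must be reconciled, because this determines how many patients the rule reaches.
- Once the withdrawal wording is removed, no other visible text says how study drug is handled after a code break. The sponsor should state this. No clinical rule is proposed here.

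The cost is two reworded sentences, the matching change to the printed card, and a flag in the dataset. No visits are added beyond those planned.

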5.5 Drug Distribution

Registration: All drugs of each site will be stored in one place and managed by a specially-assigned person. The distribution and reclaiming should be registered.

Sequence: the investigator obtain the random no. and drug no. of the subject according to the visiting sequence of the qualified subjects in each study center, and the drug administration office dispense the study drugs of corresponding drug no.

Distribution: The subjects are randomized to the test group (istaroxime) and control group (placebo) in a ratio of 2:1. All study drugs are accompanied by emergency envelopes of corresponding numbers and the emergency envelopes are kept by the principal investigator in attending site.

The drugs should be given to the subjects according to their drug numbers, and shouldn't be chosen. The random numbers should remain unchanged during the study. Each subject will be provided with a random number and sufficient study drugs. The investigator should fill in the Drug Distribution Registration Form exactly in time.

Storage: The study drugs are stored, administrated and distributed by each site. The drugs should be stored hermetically in the shade.

Remaining Drugs: If the drugs remain because patients do not take them on time, or quit midway, or the treatment changes, the drugs should be reclaimed and recorded in detail.

5.6 Dosage Regimen

Istaroxime, in powder form, will be provided in glass vials. NaCl 0.9% bags for preparation of the 4 x 50ml infusion over 24 hours, will be provided by the Center. The infusion pumps, sets, filters and connections will be provided by the research center.

Preparation of the solution for infusion will be performed by a physician or a pharmacist of the Pharmaceutical Services Division, in the presence of a suitably qualified witness according to the randomization code. A record for the preparation of the infusion will be kept for each patient according to the research center's standard operating procedure and will be approved by the Sponsor before first dosing. Stability data available support the infusion of the mixed preparation over 6 hours.

The istaroxime vials will be handled according to the manufacturer's specifications to ensure that the products are appropriately mixed prior to infusion.

In order to calculate the amount of istaroxime given to each patient in each cohort, the body weight will be determined to one decimal place. The body weight recorded on Day 1 at predose will be used for calculation of doses of istaroxime for each cohort.

5.6.1 Method of administration and compliance

Istaroxime and placebo will be provided as kits containing 4 study drug boxes. Each study drug box will contain 4 glass vials (see section 5.3). The infusion solution will be administered via a syringe pump. The exact istaroxime dose to be administered will be calculated according to patient body weight and will be modulated by the infusion rate (see Appendix A: infusion rates)

On the treatment day, a solution for infusion will be prepared every 6 hours (with 4 vials) and will be administered to the patient via the syringe pump.

The procedure for preparation of a 6-hour infusion is the following:

- 1. Check that the *Study Drug Box* # displayed on the kit is the one that has been allocated to the patient;
- 2. Select one of the 4 study drug boxes;
- 3. Remove the flip offs from the containers contained in the box;
- 4. Reconstitute each of the 4 vials with 5 mL of saline, taken from the NaCl 0.9% bag (supplied by the local center) that will be utilized for the preparation of the infusion solution, according to instructions in leaflet;
- 5. Draw completely the clear solution from the 4 reconstituted vials into a single 50 mL syringe;
- 6. Remove 30 ml of saline from the NaCl 0.9% bag with the same syringe used for the reconstitution of the 4 vials in order to obtain a total volume of 50 ml (20 ml of the 4 vials+30 ml of saline from the NaCl 0.9 % bag)
- 7. Mix the whole content of the syringe

- 8. Invert the syringe carefully 4 times and connect the syringe to the infusion line;
- 9. Prime the infusion line to the most proximal point nearest to the catheter;
- 10. Start the infusion pump at the pre-determined dosing time for the patients; Calculate the catheter volume according to the indications reported in the Section 14 of Operation Manual
- 11. Modulate the infusion rate according to patient weight (see Appendix A: Infusion rates). Syringe infusion time is 6 hours.
 - The infusion syringe must be clearly labeled with the investigational product name, the study number, and the patient number.
 - A pre-printed label is available inside the Study Drug Box. In case of use, the *Patient Screening or Randomization #* has to be added by the person preparing the investigational product.

Under close supervision, the investigational product will be continuously infused intravenously in a vein at high blood flow.

In case of clotting of a line, the infusion tube has to be disconnected from the PAC and immediately connected with the infusion line available on the introducer to continue investigational product infusion.

Treatment compliance will be verified by direct visual supervision at dosing by the Investigator or his/her designee. Drug accountability records will be kept as outlined in section 15.1.

In case of a damaged study drug box, a broken vial, or for any need for replacement of one of the 4 study drug boxes within the kit, the Investigator must discard the entire study drug box, and obtain a replacement box using the study drug box number retrieved from the replacement list.

5.7 Concomitant Medication

All oral treatments, are permitted during the study with the exception of positive inotropic agents.

Dosage of oral HF medications must remain stable for at least 6 hours before study entry, during the entire treatment period (24-hour infusion), until 72 hours (on Day 4) after the start

of infusion on Day 1. Concomitant medications should be administered in the prerandomization phase and after at least 6 hours from the initiation of study drug infusion, if possible.

Intravenous diuretics administered during the screening period to stabilize the patient's condition will be permitted during the treatment period at stable doses, unless changes are required due to clinically relevant variations of the patient's condition.

Any introduction of new drugs or increase of the dosage of oral or i.v. medications for the treatment of heart failure, during treatment and till the 72 hours after the start of infusion (on day 4), will be considered as "rescue medication".

Patient supplementation of magnesium or potassium, prior to randomization, will not be considered as a change of the standardized therapy but just as a supplementation to maintain serum electrolytes within the normal ranges.

Administration of prior medications (i.e. drug treatments administered during the last month) and concomitant medications/therapies (i.e. medications ongoing at admission time and with a start date between admission to the research center and Day 4 or discharge) must be reported on the appropriate medication pages of the CRF, including dosage information, dates and time of administration and reasons for use. The international non-proprietary name and the trade name in brackets should be used for concomitant medications. The total daily dose or the stat dose, if appropriate, should also be reported. Rescue therapies will be recorded on the specific rescue medication page, recording the same information as for concomitant therapies, plus the time of administration of each single dose.

In case an inotrope should be necessary as rescue medication during the investigational product infusion period, the investigational product infusion should be terminated.

6. CLINICAL ENDPOINTS

6.1 Efficacy Endpoints

1. Primary efficacy end-points:

• Change from baseline to 24 hours after infusion start (treatment period Day 1) in the E/Ea ratio assessed by tissue Doppler.

2. Secondary efficacy end-points:

- Change from baseline to 24 hours in the treatment period Day1 (addressing the differences between the changes at 6 and 24 hours from baseline) of the following Echo-Doppler parameters:
 - LV Ejection Fraction (EF)
 - LV end systolic and end diastolic volumes
 - Stroke volume index (SVI)

- E, A and E/A ratio
- Change from baseline to 24 hours in the E/Ea ratio assessed by tissue Doppler (difference between the changes at 6 and 24 hours from baseline)
- Others Tissue Doppler parameters such as Sa, Da and Aa
- Changes in dyspnea assessed at 3, 6, 12, 24, 48 hours after infusion start by Visual Analog Scale (VAS) (including only patients presenting dyspnea at baseline);
- Area under the curve (AUC) on changes in dyspnea assessed at 3, 6, 12, 24, 48 hours after infusion start by VAS (including only patients presenting dyspnea at baseline);
- Changes in BNP from baseline at 24 hours;
- Proportion of patients with hospital readmissions or emergency visits for cardiovascular reasons by Day 30;
- Proportion of patients with episodes of worsening HF defined by the need to increase the dose or reinitiate i.v. therapy with diuretics and/ or other inotropic agents during the hospitalization;
- Length of hospitalization.

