4. STUDY POPULATION

A total of 96 Chinese and 24 Italian patients hospitalized with ADHF not requiring inotropic therapy at inclusion into the study (according to the opinion of the Investigator) and not presenting signs and/or symptoms of severe low output state or peripheral hypo perfusion will be randomized.

To be included into the study, patients have to fulfill eligibility criteria both at their admission to the hospital (screening criteria) and just prior to randomization (randomization criteria).

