4.2 Exclusion criteria

Any of the following criteria established **at screening** would render a patient ineligible for the study:

- 1. Pregnant or breast-feeding women (women of child bearing potential must have the results of a negative pregnancy test recorded prior to study drug administration)
- 2. Current (within 6 hours prior to screening), during the screening or planned (if the patients was treated with dopamine or nitrates iv infusion) (through the completion of study drug infusion) treatment or within 12 hours prior to screening if the patient was treated with other iv. vasodilators or other inotropic agents and vasopressors,
- 3) Current or need of mechanical support (intra-aortic balloon pump, endotracheal intubation, mechanical ventilation, or any ventricular assist device),
- 4. Ongoing treatment with oral digoxin. Patient treated with digoxin cannot be randomized. (However, if digoxin treatment has been stopped during the last week before signing informed consent form and the digoxin plasma level is < 0.5 ng / ml, patient may be randomized; if the patients have stopped digoxin for more than one week before signing informed consent form, it is not necessary to test the plasma level of digoxin.)
- 5. History of hypersensitivity to the study medication or any related medication;
- 6. Diagnosis of cardiogenic shock within the past month;
- 7. Acute coronary syndrome or stroke within the past 3 months;
- 8. Coronary artery bypass graft or percutaneous coronary intervention within the past month or planned in the next month;
- 9. Primary hypertrophic or restrictive cardiomyopathy or systemic illness known to be associated with infiltrative heart disease;
- 10. Cor pulmonale or other causes of right-sided HF not related to left ventricular dysfunction;
- 11. Pericardial constriction or active pericarditis;
- 12. Atrial fibrillation with marked irregularities of heart rhythm (Inclusion criteria 8 can not be met);

- 13. Life threatening ventricular arrhythmia or ICD (implantable cardioverter defibrillator) shock within the past month;
- 14. Presence of a CRT (cardiac resynchronization therapy), ICD or pacemaker devices implanted within the past month;
- 15. Valvular disease as the primary cause of HF (except those corrected by surgery without obstruction in left ventricle output);
- 16. Heart rate > 120 bpm or < 50 bpm
- 17. Acute respiratory distress syndrome or ongoing sepsis;
- 18. Fever $>38^{\circ}$

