8. EFFICACY ASSESSMENTS

Change from baseline to 24 hours after infusion start in the E/Ea ratio assessed by tissue Doppler will be assessed as primary end-point. Other echocardiographic parameters (LVEF, LV end diastolic and end systolic volumes, SVI, E/A ratio, other Tissue Doppler parameters such as Sa, Da and Aa) will be assessed as secondary end-points. These parameters will be assessed also at 48 hours as further exploratory analyses.

Dyspnoea will be assessed at baseline using a 100 mm VAS scale. Further assessments will be repeated at 3, 6, 12, 24 and 48 hours after the start of drug infusion only in patients presenting dyspnoea at baseline.

NT-proBNP will be measured by the local laboratory only for evaluation and screening inclusion. While at baseline, at 24 hours after infusion start (day 2), on Day 3, at day 4 or at discharge) and at day 30, NT-proBNP will be measured by the central laboratory

Episodes of worsening HF, defined by the need to increase the dose or reinitiate i.v. therapy with diuretics and/ or other inotropic agents during the hospitalization, will be recorded.

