# 3.2.2 Secondary Endpoints

The secondary efficacy endpoints are the following:

- Change from baseline to 24 hours in the treatment period Day 1 (addressing the differences between the changes at 6 and 24 hours from baseline) of the following Echo-Doppler parameters:
  - o Left Ventricular Ejection Fraction (LVEF)
  - o LV end systolic and end diastolic volumes
  - o Stroke volume index (SVI), and CI
  - o E, A and E/A ratio
  - o Ea and TAPSE
- Change from baseline to 24 hours in the E/Ea ratio assessed by tissue Doppler (difference between the changes at 6 and 24 hours from baseline)
- Others tissue doppler parameters such as Sa;
- Changes in dyspnoea assessed at 3, 6, 12, 24, 48 hours after infusion start by Visual Analog Scale (VAS) (including only patients presenting dyspnoea at baseline);

1.0/30/10/2018 Page 8 of 28

- Area under the curve (AUC) on changes in dyspnoea assessed at 3, 6, 12, 24, 48 hours after infusion start by VAS (including only patients presenting dyspnoea at baseline);
- Changes in Brain Natriuretic Peptide (BNP) from baseline at 24 hours;
- Proportion of patients with hospital readmissions or emergency visits for cardiovascular reasons by Day 30;
- Proportion of patients with episodes of worsening heart failure defined by the need to increase the dose or reinitiate i.v. therapy with diuretics and/ or other inotropic agents during the hospitalization;
- Length of hospitalization.

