# Patients with episodes of worsening heart failure during the hospitalization

The number and percentage of patients with episodes of worsening heart failure during the hospitalization will be summarized at Days 2, 3 and 4 by treatment groups using descriptive statistics.

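### Worsening HF, as literally worded, counts a dose increase or restart of i.v. diuretic or inotrope but not a first inotrope start, which Protocol 5.7 treats as rescue

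*Protocol*

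**What the plan says.** Protocol 6.1 lists, among the secondary efficacy endpoints, the proportion of patients with worsening HF, "defined by the need to increase the dose or reinitiate i.v. therapy with diuretics and/ or other inotropic agents during the hospitalization". The synopsis and Protocol 14.2 use the same triggers. Protocol 8 repeats them ("Episodes of worsening HF, defined by the need to increase the dose or reinitiate i.v. therapy with diuretics"), and so does SAP 3.2.2 ("episodes of worsening heart failure defined by the need to increase the dose or reinitiate i.v. therapy with diuretics"). SAP 7.7.2 adds no derivation rule and says only that the result "will be summarized at Days 2, 3 and 4 by treatment groups using descriptive statistics".

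On inotropes at entry, Protocol 4 describes patients as "not requiring inotropic therapy at inclusion into the study". Exclusion criterion 2 in Protocol 4.2 bars i.v. dopamine or nitrates within 6 hours of screening, and use "within 12 hours prior to screening if the patient was treated with other iv. vasodilators or other inotropic agents and vasopressors". Inclusion criterion 3 requires a need for i.v. diuretic at admission.

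Protocol 5.7 defines rescue medication with a broader trigger: "Any introduction of new drugs or increase of the dosage of oral or i.v. medications for the treatment of heart failure", from the treatment period to 72 hours after infusion start. Rescue drugs go on their own CRF page with the time of each dose. The same section foresees an inotrope as rescue during the infusion and says that the study infusion should then end.

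**The concern.** The endpoint names inotropes, but its two triggers both presuppose an inotrope that the patient is on or has been on before. In a population selected for not needing one, the usual rescue inotrope is a first start, and that is the case the wording leaves out. The same event can then be rescue medication under Protocol 5.7, end the study infusion, and still be scored as no worsening HF in the efficacy table.

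This is the only in-hospital clinical event among the efficacy endpoints: readmissions and emergency visits come after discharge, length of stay is a duration, and mortality is a safety endpoint. Sites in two countries may also read *reinitiate* differently, which would make the count inconsistent.

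**Working it through.** Neither document gives an expected rate, power or sample size for this endpoint, so there is no figure to reproduce. The check is a comparison of texts, followed by the weight of one patient.

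**Step 1: each kind of i.v. escalation under the two rules.**

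| Escalation after the infusion starts | Literal worsening-HF definition | Rescue under Protocol 5.7 (to 72 hours) |
|---|---|---|
| Increase of i.v. diuretic dose for HF | Counts | Yes |
| First inotrope start together with an i.v. diuretic increase or restart | Counts, through the diuretic | Yes |
| Inotrope restarted after earlier use | Counts | Yes, as a newly introduced drug |
| First inotrope start, diuretic unchanged | Not met: neither an increase nor a restart | Yes, as a newly introduced drug |

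**Step 2: how much is left of the inotrope limb.** No patient should enter on an inotrope, so at entry there is no dose to increase. A true restart needs earlier use outside the 6- or 12-hour window before screening, which the criteria allow. A patient who gets a first inotrope and later has its dose raised, or has it stopped and resumed, would count at that later step but not at the start. Read literally, then, the limb is nearly empty for the event that Protocol 5.7 foresees.

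**Step 3: is it repaired elsewhere?** No. None of the statements of the endpoint includes a first start. SAP 7.7.2 gives no derivation, and nothing in either document links the rescue page to this endpoint.

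**Step 4: the weight of one patient.** Each istaroxime arm has 40 patients and each cohort has 20 on placebo (Protocol 3). SAP 7.4 pools placebo for non-echocardiographic endpoints, giving 20 + 20 = 40.

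- Istaroxime arm or pooled placebo: 1/40 = 2.5 percentage points per uncounted patient.
- Placebo in a single cohort: 1/20 = 5 percentage points.

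The number of such patients cannot be derived from the documents.

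**The case against.** The strongest reply is that the text is ambiguous and does not clearly exclude a first start. The phrase can be read as going back to i.v. heart failure therapy of either class, and naming inotropes for patients who do not need them at entry suggests that starting one was meant to count. This stands as a reading of intent. It does not remove the problem, because an event definition with two readings needs one of them written down.

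Second, a reader might infer that a first inotrope is the likely form of rescue, or that the endpoint misses the most severe deteriorations and keeps the mildest. The documents support neither. They give no likelihoods. All patients are admitted needing i.v. diuretic, so a diuretic increase or restart, which counts, is at least as plausible. A patient who gets both is counted.

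Third, a reader might take the absence of new vasodilators, vasopressors and mechanical support as the same error. It is not. Adding them would make a different composite, and nothing requires the endpoint to equal rescue medication, which also covers oral drugs.

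Fourth, these events are not lost to the trial. New HF drugs to 72 hours are on the rescue page, and serious deteriorations may reach the adverse-event tables. That is true, but it does not correct the efficacy table.

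Finally, the rescue definition stops at 72 hours while the endpoint refers to the hospitalization. This matters little for the planned table, which covers Days 2, 3 and 4. The CRF is not among the documents, so how sites actually score an episode cannot be checked.

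**Conclusion.** The point holds as a defect in the literal wording. A first start of an i.v. inotrope without an i.v. diuretic increase or restart falls outside the definition, while Protocol 5.7 treats it as rescue. The conclusion assumes that *reinitiate* keeps its ordinary meaning of starting again, and that most rescue inotropes would be first starts, which follows from the entry criteria but is not guaranteed by the 6- and 12-hour windows.

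The size is 2.5 percentage points per uncounted patient in a group of 40. The total effect and its direction between arms are unknown. The consequence is limited: the endpoint is secondary and descriptive, so no test, power statement or stopping rule rests on it. It is still worth correcting, because the present rule can score a deterioration that ends study treatment as no event.

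**What to change.** Reconcile Protocol 5.7, 6.1, 8 and 14.2 (and the synopsis) with SAP 3.2.2. Define an episode as the need to *initiate, reinitiate or increase the dose of i.v. diuretics and/or inotropic agents for heart failure* during the hospitalization. In SAP 7.7.2, state that the endpoint is derived from the rescue and concomitant-medication pages already collected, and report the diuretic and inotrope components separately beside the total. Settle this before unblinding.

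New i.v. vasodilators or vasopressors may be tabulated descriptively from the same pages but need not enter the endpoint. Mechanical support is not a medication and is left out of this change.

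The cost is a wording change in both documents and one derivation rule. The event rate may be slightly higher in all arms. Only what is counted changes, not how patients are managed.
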